4. LIST OF ABBREVIATIONS

Abbreviation	Explanation
ABPI	Association of British Pharmaceutical Industry
ACE	Angiotensin Converting Enzyme
ADR	Adverse Drug Reaction
AE	Adverse Event
ALP	Alkaline Phosphatase
ALT	Alanine Aminotransferase
ANCOVA	Analysis of covariance
ANOVA	Analysis of variance
AST	Aspartate Aminotransferase
BMI	Body Mass Index
BP	Blood Pressure
CI	Chief Investigator
CK	Creatine Kinase
C _{max}	Maximum plasma concentration
CRO	Clinical Research Organisation
CRP	C-reactive Protein
CSR	Clinical Study Report
DHP	Data Handling Plan
EC	Ethics Committee
ECG	Electrocardiogram
eCRF	electronic Case Report Form
ED	Erectile Dysfunction
EF	Erectile Function
ePRO	electronic Patient-Reported Outcomes
EU	European Union
FAS	Full Analysis Set
FMD	Futura Medical Developments Ltd
GAQ	Global Assessment Questionnaire
GCP	Good Clinical Practice
GGT	Gamma-Glutamyl Transpeptidase
GMP	Good Manufacturing Practice
GTN	Glyceryl Trinitrate
HBc	Hepatitis B Core antibodies
HbsAG	Hepatitis B Surface Antigen

HCV	Hepatitis C Virus
HIV	Human Immunodeficiency Virus
HR	Heart Rate
IB	Investigator's Brochure
ICF	Informed Consent Form
ICH	International Council for Harmonisation
IgG	Immunoglobulin G
IgM	Immunoglobulin M
IIEF	International Index for Erectile Function
IMP	Investigational Medicinal Product
IP	Inorganic Phosphate
IUD	Intrauterine Device
IUS	Intrauterine System
IVRS	Interactive Voice Response System
IWRS	Interactive Web Response System
LDH	Lactate Dehydrogenase
LS	Least-Squares
MCID	Minimal Clinically Important Difference
MedDRA	Medical Dictionary for Regulatory Activities
MNAR	Missing Not At Random
NIH	National Institutes of Health
NO	Nitric Oxide
NSAID	Non-Steroidal Anti-Inflammatory Drug
OLAS	Open-Label Analysis Set
PD	Pharmacodynamic
PDE-5	Phosphodiesterase type 5
PGE 1	Prostaglandin E1
PGI-C	Patient Global Impression of Change
PGI-S	Patient Global Impression of Severity
PI	Principal Investigator
PK	Pharmacokinetic
PP	Per Protocol
PT	Preferred Term
QA	Quality Assurance
QC	Quality Control
QP	Qualified Person

ROC	Receiver Operating Characteristics
SAE	Serious Adverse Event
SAP	Statistical Analysis Plan
SD	Standard Deviation
SE	Standard Error
SEAR	Self-Esteem And Relationship questionnaire
SEP	Sexual Encounter Profile
SOC	System Organ Class
SPC	Summary of Product Characteristics
SUSAR	Suspected Unexpected Serious Adverse Reaction
T _{1/2}	Terminal elimination half-life
T _{max}	Time to reach C _{max}
TMF	Trial Master File
ULN	Upper Limit of Normal
US	United States
w/w	Weight in weight

5. STUDY SYNOPSIS

Protocol Ref: FM57	Study Product: MED2005
Title of the Study: A Phase III, dose-ranging, multi-centre, randomised, double-blind, placebo-controlled, home use, parallel group clinical trial of topically-applied glyceryl trinitrate (GTN) for the treatment of erectile dysfunction (ED) with an open label extension	
Chief Investigator: [name]	
Sites: Approximately 50 investigational sites in countries including Poland, Hungary, Czech Republic, Slovakia, Georgia, Russia, Ukraine, Bulgaria and Latvia.	
Study Period (planned): 2018–2020	Clinical Phase: III
Objectives:	
Primary Objective	

 To demonstrate the efficacy of MED2005 versus placebo in male subjects clinically diagnosed with ED using the erectile function (EF) domain of the International Index for Erectile Function (IIEF), the Sexual Encounter Profile (SEP) Question 2 and the SEP Question 3. The primary objective will be addressed by estimating the following estimand: difference between treatment policies (each MED2005 dose versus placebo) in all subjects who met the study inclusion/exclusion criteria and who were randomised and attempted intercourse post-randomisation at least once, assessed via the change compared to baseline in EF [IIEF-EF], the ability to achieve vaginal penetration [SEP Question 2] and the ability to have successful intercourse [SEP Question 3] over 12 weeks of treatment 	
Secondary Objectives	

 To evaluate the efficacy of MED2005 in male subjects using the Self-Esteem And Relationship (SEAR) questionnaire for men and women, the Global Assessment Questionnaire (GAQ), the additional domains of the IIEF, the Patient Global Impression of Severity (PGI-S), the Patient Global Impression of Change (PGI-C) as well as subjective measures of the time of onset and duration of action (erection) & erection hardness and questions on usage and application of MED2005 To evaluate the long-term (up to 12 months) efficacy of MED2005 To evaluate the safety of MED2005 using adverse events (AEs) and standard physico-chemical assessments 	
Study Design:	
A Phase III, dose-ranging, multi-centre, randomised, double-blind, placebo-controlled, home use, parallel group clinical study to evaluate the efficacy and safety of MED2005, a topically applied GTN gel for the treatment of ED. The study will include a screening period, a double-blind phase and an open-label extension phase.	
Screening Period: Subjects will be screened for eligibility during a screening period between Day –43 and Day –1. The IIEF questionnaire will be completed by the subject at the start of the screening period at the first site visit (Visit 1) and the EF domain of the IIEF (IIEF-EF; i.e. Questions 1–5 and 15) will be used to determine pre-screening eligibility of the subject. A score of ≤ 25 will be acceptable for inclusion in the screening period of the study. Both the male subject and his female partner will be required to attend Visit 1. Subject and partner training in the use of questionnaires and IMP application will be given at this visit.	
During the screening period, subjects and their partners are required to make a minimum of four attempts at sexual intercourse within a 4-week period (without treatment). They will be asked to complete questionnaires to record their experiences after each sexual intercourse attempt (using the SEP [male subjects and their female partners]) and at the end of the 4-week period (using the IIEF and PGI-S [male subjects only] and SEAR [male subjects and their female partners]) according to a prescribed schedule of questionnaires. Subjects who cannot comply with the minimum number of intercourse attempts or who exceed 25 on the IIEF-EF at the end of the screening period will be excluded from the study.	
Double-Blind Phase: Eligible subjects will participate in the double-blind phase, comprising a 12-week treatment period (Visits 2, 3, 4 and 5) and a 1-week follow-up visit (Visit 6). The subject and his female partner will be required to attend Visit 2 at the start of the double-blind phase.	
During the treatment period subjects will be randomly allocated to receive placebo or one of three doses of MED2005 (0.6 mg GTN, 1.2 mg GTN, 1.8 mg GTN). Subjects will be divided into sub-groups based on their baseline ED severity scores (from the end of the screening period): mild (IIEF-EF domain score of 17–25), moderate (IIEF-EF 11–16) or severe (IIEF-EF ≤ 10). The number of subjects in each of the three baseline ED severity groups will be monitored during the trial in order to have approximately equal numbers in each group.	

At home, subjects or their partners should apply the investigational medicinal product (IMP) immediately prior to sexual intercourse and make at least four intercourse attempts in each of the three 4-weekly periods during treatment (Weeks 1–4, 5–8 and 9–12). The subjects and their partners will be asked to complete questionnaires using electronic patient-reported outcomes (ePRO) to record their experiences after each sexual intercourse attempt (using the SEP questionnaire and the onset and duration of action [erection] and erection hardness questions at home [male subjects and their female partners]), and at the end of each of the three 4-week periods during treatment (using the IIEF, PGI-S and PGI-C questionnaires [male subjects only], and the SEAR and GAQ questionnaires [male subjects and their female partners]; to be completed at site visits for subjects and at home for their partners if preferred).

Subjects and their female partners will be monitored for AEs by being asked to complete 4-week diaries at home of untoward signs and symptoms as they experience them (i.e. in real time) throughout the duration of the double-blind phase of the study (from signing of informed consent until the follow-up assessment at Visit 6). The diaries will be reviewed at each study visit.

Subjects will be asked to return to the study site at the end of each of the three 4-week (± 1 week) periods during treatment (i.e. at Visits 3, 4 and 5) to return used and unused IMP, to enable the clinical staff to check compliance and to assess subject health status, including assessment of any AEs and recording concomitant medications. These visits will be optional for the female partners. Subjects and their female partners will be required to attend a follow-up visit (Visit 6) 7 days (± 2 days) after the Week 12 visit (Visit 5).

At the end of the double-blind phase, during Visit 6, subjects and their female partners will be invited to take part in the open-label extension phase at the 0.6% MED2005 (1.8 mg GTN) dose level. Participation in the extension phase will be at the discretion of the individual subject and his partner and if there are still available places. Recruitment will continue until approximately 450 subjects and their female partners have consented. The remaining subjects will be discharged from the study.

Open-Label Extension Phase: The open-label extension phase will comprise 12-months treatment for eligible subjects, with visits every 3 months. For each 3-month period subjects will be dispensed 12 tubes per month (36 tubes at each visit) to allow them to use the tubes as they require. Male subjects will be asked to complete the SEP questionnaire to record their experiences after each sexual intercourse attempt as and when they occur. At each site visit male subjects will be asked to complete the IIEF questionnaire to cover the previous 1 month. Subjects and their female partners will be monitored for AEs by completing diaries of untoward signs and symptoms as they experience them (i.e. in real time) throughout the duration of the open-label extension phase.

Once they have entered the open-term extension phase, male subjects will be asked to return to the study site every 3 months (at Day 180 [Visit 7], Day 270 [Visit 8], Day 360 [Visit 9] and Day 450 [Visit 10]) to enable the clinical staff to check AEs and concomitant medications (in the diaries), SEP questionnaire completed after each intercourse attempt to cover each 3-month period, IIEF to cover previous 1-month period and compliance on IMP usage. Vital signs and a penis examination will be undertaken at each 90 day visit. An electrocardiogram (ECG) will be done at 12 months (Day 450). Visits during the open-label extension phase will be optional for the female partners.

Number of Subjects:

Double-Blind Phase: It is planned to randomise and treat 250 male subjects for each of the four treatment groups, clinically diagnosed with ED, and their female partners (total N = 1000).

Open-Label Extension Phase: It is planned to include a total of 450 male subjects who have completed the double-blind phase of the study, and their female partners.

Diagnosis and Main Criteria for Admission:

Double-Blind Phase: Male subjects aged 18–70 years with a confirmed clinical diagnosis of ED for more than 3 months (according to the National Institutes of Health Consensus Statement 'the inability to achieve or maintain penile erection sufficient for satisfactory sexual performance at least once'), verified by the IIEF-EF domain (a score of ≤ 25 points at the end of the screening period) and involved in a continuous heterosexual relationship with their partner for at least 6 months.

Exclusion criteria include: any significant cardiovascular, pulmonary, hepatic, renal, gastrointestinal, haematological, endocrinological, metabolic, neurological or psychiatric disease; any history of an unstable medical or psychiatric condition or using any medication that, in the opinion of the Principal Investigator (PI), is likely to affect the subject's ability to complete the study or precludes the subject's participation in the study.

Open-Label Extension Phase: Subjects who complete the double-blind phase, were compliant to study procedures and who consent to the open-label extension phase.

Exclusion criteria include: Subsequent to recruitment into the double-blind phase of the study, the development of any significant or serious cardiovascular, pulmonary, hepatic, renal, gastrointestinal, haematological, endocrinological, metabolic, neurological or psychiatric disease which, in the opinion of the PI, renders the subject unfit to continue in the open-label extension phase of the study.

Study Treatments and Mode of Administration:

Double-Blind Phase: Subjects will be randomly allocated in a 1:1:1:1 ratio to receive one of the following gel treatments according to a parallel group design (i.e. subjects will receive one treatment only):

- MED2005 0.2% (w/w) GTN gel to deliver a 0.6 mg dose of GTN
- MED2005 0.4% (w/w) GTN gel to deliver a 1.2 mg dose of GTN
- MED2005 0.6% (w/w) GTN gel to deliver a 1.8 mg dose of GTN
- Placebo vehicle

Randomisation will be carried out on Day 1 of the treatment period of the double-blind phase (Visit 2) according to an interactive voice/web response system (IVRS/IWRS), stratified by baseline ED severity. No stratification by site will be done. During the treatment period, the subjects or their partners will be required to topically apply a single dose (approximately 300 mg) to the glans of the penis and rub in for at least 15 seconds (to ensure thorough distribution of the gel and promote penetration of the active substance) immediately prior to sexual intercourse. Subjects will be asked to leave a washout period of at least 12 hours before the next attempt at sexual intercourse using the IMP gel.

Open-Label Extension Phase: All subjects will receive treatment with MED2005 0.6% (w/w) GTN gel to deliver a 1.8 mg (0.6%) dose of GTN. The gel is to be used as described above for the double-blind phase.

Reference Treatment and Mode of Administration:

Placebo vehicle gel, identical in appearance to the three active MED2005 gels. The placebo gel will be administered as a single dose in the same way and at the same volume as MED2005.

Duration of Treatment:

Double-Blind Phase: Eligible subjects will participate in a 12-week treatment period (Visits 2, 3, 4 and 5) and a 1-week follow-up visit (Visit 6). Subjects will be asked to apply the IMP immediately prior to sexual intercourse and to make at least four intercourse attempts in each of the three 4-weekly periods during treatment (Weeks 1–4, 5–8 and 9–12).

Open-Label Extension Phase: Eligible subjects will participate for a further 360 days of treatment (Visits 7, 8, 9 and 10). Subjects will use the IMP immediately prior to sexual intercourse as they require.

Criteria for Evaluation:**Efficacy Assessments:**

Efficacy will be evaluated using questionnaires (IIEF, SEP, SEAR, GAQ, PGI-S, PGI-C) as well as subjective measures of time of onset and duration of action (erection) and erection hardness. The co-primary efficacy outcomes will be the IIEF-EF domain, SEP Question 2 and SEP Question 3, completed by the male subjects. Information on usage and application of the gels will be evaluated.

Safety Assessments:

Safety will be evaluated throughout the double-blind phase using standard assessments including physical examinations and visual examination of the penis, vital signs (blood pressure [BP], heart rate [HR], body temperature), standard clinical laboratory safety tests (haematology, biochemistry, urinalysis), 12-lead ECGs and monitoring of AEs and concomitant medications with paper diaries (potential partner AEs will be captured at site visits or by telephone). Safety will be evaluated throughout the open-label extension phase by monitoring of AEs and concomitant medications with paper diaries (potential partner AEs will be captured at site visits or by telephone), monitoring of vital signs, ECGs, and visual examination of the penis.

Statistical Methods:

In general, safety and efficacy variables will be presented by means of descriptive statistics and figures, as appropriate, by treatment (active at each dose level and placebo) and by time point and gender, if applicable.

A Bonferroni correction will be used to take into account that there are three active versus placebo comparisons; i.e. all p-values resulting from comparing the three different MED2005 doses (0.6 mg GTN, 1.2 mg GTN, 1.8 mg GTN) versus placebo will be multiplied by three and statistical significance will then be declared if $p < 0.05$. Corresponding Bonferroni corrected 95% confidence intervals will be produced.

Efficacy Analyses:

Double-Blind Phase: Primary and secondary analyses will be performed on the Full Analysis Set (FAS; all randomised subjects who used medication at least once).

The co-primary efficacy endpoints, assessed in the male subjects, are:

- The change from baseline of the average of the Week 4, Week 8 and Week 12 IIEF-EF domain scores
 - The change in percentage of sexual intercourse attempts in which subjects were able to insert their penis into their partner's vagina (SEP Question 2) between baseline and the 12 week treatment period
 - The change in percentage of sexual intercourse attempts in which subjects were able to maintain an erection of sufficient duration to have successful intercourse (SEP Question 3) between baseline and the 12 week treatment period
-

The primary objective will be assessed by testing hypotheses for each MED2005 group (0.6 mg GTN, 1.2 mg GTN or 1.8 mg GTN) separately. The basic statistical model for the primary analysis for all three co-primary endpoints is an analysis of covariance (ANCOVA) including terms for treatment group, site and baseline (as a continuous variable). Baseline ED severity (mild, moderate or severe, based on Visit 2 IIEF-EF) will be included in the analysis of the SEP questions, and will be included in the analysis of IIEF-EF as a sensitivity analysis. The estimated treatment means and differences (MED2005 versus placebo) will be reported as part of this analysis. The objective is for all co-primary endpoints to show superiority of MED2005 to placebo in order to conclude a significant result. No adjustment for multiplicity of the error probability for the individual co-primary endpoints is required. However, the three co-primary endpoints will still be considered in a hierarchy of their importance: IIEF-EF domain, SEP Question 3 and SEP Question 2.

The following secondary efficacy analyses will be performed in a supportive way to describe the effect of treatment:

- The analysis of the three co-primary endpoints will be repeated in the three pre-specified subgroups of ED severity: mild, moderate and severe
- The change in the IIEF-EF domain, SEP Question 2 and SEP Question 3 at each 4-week visit will be analysed
- Responder analyses assessing the proportion of subjects with a specific increase in the IIEF-EF domain from baseline, using a different responder definition defined separately for each baseline severity group
- Responder analyses for SEP Questions 2 and 3 will be conducted in the same way as for the IIEF-EF
- Responder analyses will also be conducted using responder thresholds (that represent meaningful within-patient changes) in the three co-primary endpoints that are determined using anchor-based methods. The thresholds will be defined using a suitable set of data from this study prior to study unblinding.

The following secondary efficacy analyses will be conducted in a more exploratory way:

- The GAQ will be analysed via logistic regression including terms for treatment group, site and baseline ED severity (categorical variable)
- The change in the other domains of the IIEF questionnaire, the other SEP questions (Questions 1, 4 and 5), the overall SEAR questionnaire score, the scores in the two subdomains of the SEAR questionnaire (sexual relationship satisfaction and confidence), the PGI-S at time points 4, 8 and 12 weeks will be analysed using ANCOVA as described for the primary endpoint analysis. The PGI-C will be analysed using an analysis of variance (ANOVA)
- Subjective measures of the time of onset and duration of action (erection) and erection hardness will be analysed using an ANCOVA model fitted to the average of Wilcoxon Rank Scores
- Usage and application question responses will be summarised by treatment group

All efficacy assessments provided by the female partners will be analysed using the same statistical models as for the male subjects.

Open-Label Extension Phase: Efficacy assessments will be summarised, including (where applicable) changes from baseline, where the baseline assessments are the ones prior to the double-blind phase.

Safety Analyses

Summary statistics will be presented for scheduled assessments and change from baseline for vital signs, ECGs and clinical laboratory safety tests.

Dosing duration and frequency will be summarised.

AEs will be listed by system organ class (SOC) and preferred term (PT) classifications assigned to the event using the Medical Dictionary for Regulatory Activities (MedDRA; Version 20.1 or higher). The number of AEs and number (and %) of subjects with AEs will be summarised by SOC and PT. In addition, AEs will be summarised by severity, relationship to treatment, time to onset (from the last dose of IMP prior to AE start date) and duration (offset).

Listings will be presented of serious adverse events (SAEs) and AEs leading to withdrawal.

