14.5.3 Primary Analysis

The co-primary efficacy endpoints, assessed in the male subjects, are:

1. The change from baseline of the average of the Week 4, Week 8 and Week 12 IIEF-EF domain scores
2. The change in percentage of sexual intercourse attempts in which subjects were able to insert their penis into their partner's vagina (SEP Question 2) between baseline and the 12 week treatment period
3. The change in percentage of sexual intercourse attempts in which subjects were able to maintain an erection of sufficient duration to have successful intercourse (SEP Question 3) between baseline and the 12 week treatment period

Baseline for the IIEF-EF score is the assessment at Visit 2, baseline for SEP Questions 2 and 3 is the percentage in the screening, treatment free, 4-week period.

The primary objective will be assessed by testing the following hypotheses for each MED2005 dose group (0.6 mg GTN, 1.2 mg GTN or 1.8 mg GTN) and each co-primary endpoint separately, using the FAS:

Null hypothesis (H0): There is no difference in the mean change from baseline in the IIEF-EF domain, SEP Question 2 and SEP Question 3 for the MED2005 treatment group compared with placebo.

$$H0: \mu (\text{MED2005}) = \mu (\text{placebo})$$

Alternative hypothesis (H1): There is a difference in the mean change from baseline in the IIEF-EF domain, SEP Question 2 and SEP Question 3 for the MED2005 treatment group compared with placebo.

$$H1: \mu (\text{active}) \neq \mu (\text{placebo})$$

Each comparison will be carried out at the two-sided 5% level of statistical significance after a Bonferroni correction (p-values multiplied by three). Efficacy will be stated if all null hypotheses for the co-primary endpoints are rejected. However, the three co-primary endpoints will still be considered in a hierarchy of their importance, with the testing order being IIEF-EF domain, SEP Question 3 and SEP Question 2.

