The statistical model for the primary analysis of the IIEF-EF will be an analysis of covariance (ANCOVA) including terms for treatment group, site and baseline (as a continuous variable). The statistical model for the primary analyses of SEP Question 2 and SEP Question 3 will be an ANCOVA including terms for treatment group, site, baseline (as a continuous variable) and baseline ED severity (categorical variable). As the endpoints are change from baseline assessment, the respective baselines for each endpoint are included in the analyses. Baseline ED severity, used as part of the randomisation scheme, is a categorical grouping of the baseline IIEF-EF and as such is not included in the primary analysis of the IIEF-EF as it already appears in the model as a continuous variable. A sensitivity analysis will be performed including baseline ED severity (categorical variable) in addition to the variables included in the primary analysis. The estimated treatment means and differences (MED2005 versus placebo) will be reported as part of this analysis.

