- The change in the other domains of the IIEF questionnaire, the other SEP questions (Questions 1, 4 and 5), the overall SEAR questionnaire score, the scores in the two subdomains of the SEAR questionnaire (sexual relationship satisfaction and confidence) and the PGI-S at time points 4, 8 and 12 weeks will be analysed using ANCOVA as described for the primary endpoint analysis for SEP Questions 2 and 3. The PGI-C will be analysed using an analysis of variance (ANOVA)
- Subjective measures of the time of onset and duration of action (erection) and erection hardness will be analysed using Wilcoxon ranks for each intercourse attempt, averaged across intercourse attempts within each 4-week period for each subject. The averaged Wilcoxon rank data will be analysed using ANCOVA as described for the primary endpoint analysis

- Usage and application question responses will be summarised by treatment group

All efficacy assessments provided by the female partners will be analysed using the same statistical models as for the male subjects.

Open-label extension phase:

Summary statistics for all efficacy measures will be given for actual values and changes from baseline (where applicable), where the baseline assessments are the ones prior to the double-blind phase. Individual components of composite scores (but not domains) will not be summarised unless otherwise stated. Individual components as well as domains will be presented in listings together with the scores used in the analysis.

Summaries of responders at each Visit will be given using the same responder definitions as per the analysis of double-blind phase.

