14.7 Sample Size

A sample size of $n = 250$ per group (total $N = 1000$) provides 90% study power to reject the null hypotheses for all three primary endpoints when comparing a MED2005 dose to placebo, using a Bonferroni corrected type I error, adjusting for three dose versus placebo comparisons. The sample size calculations were performed using EAST 6.4 in the continuous endpoint two-sample multiple comparisons multiple endpoints platform using the assumptions described below.

It is assumed that MED2005 is slightly better than alprostadil [33]. For the higher two doses alprostadil saw an improvement compared to placebo for IIEF-EF of 3.2 and 3.1 (least squares [LS] mean changes), giving an average of 3.15, for SEP Question 2 of 9.6 and 11.3 (LS mean changes), giving an average of 10.65, and for SEP Question 3 of 13.4 and 8.7 (LS mean changes), giving an average of 11.05. In Study FM53 there was a better improvement in SEP Question 3 than SEP Question 2 so the sample size assumptions take this into account. PDE 5's also appear to find SEP Question 2 more difficult to improve compared to placebo than SEP Question 3. Compared with the alprostadil results therefore it is assumed that the difference of MED2005 minus placebo for IIEF-EF is 3.2, for SEP Question 2 is 11.5 and for SEP Question 3 is 12.

Estimates of standard deviations are based on FM53 and published results from other ED treatments and are assumed to be 5.6, 33 and 33 for IIEF-EF, SEP Question 2 and Question 3, respectively [33, 34]. The differences between MED2005 and placebo for each endpoint are assumed to follow a multivariate normal distribution with the following correlation matrix, based on observed data from study FM53.

	IIEF-EF	SEP Question 2	SEP Question 3
IIEF-EF	1	0.5	0.5
SEP Question 2	0.5	1	0.6
SEP Question 3	0.5	0.6	1

For the open-label extension phase it is planned to recruit a total of 450 male subjects in order to meet ICH requirements.

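### The SEP Question 2 and 3 models use the Visit 2 IIEF-EF only as three severity groups; adding the continuous score would be a small, free gain in precision

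*Protocol*

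**What the plan says.** The synopsis (section 5, efficacy analyses) sets the covariate for the SEP endpoints: "Baseline ED severity (mild, moderate or severe, based on Visit 2 IIEF-EF) will be included in the analysis of the SEP questions". Section 14.5.3 gives the full SEP model as an "ANCOVA including terms for treatment group, site, baseline (as a continuous variable) and baseline ED severity (categorical variable").

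The same section says that each model carries its own endpoint's baseline. The continuous covariate in the SEP models is therefore the screening-period SEP percentage, and continuous IIEF-EF appears only in the IIEF-EF model. There the severity category is left out of the primary analysis, because it is a grouping of a score already in the model, and is added back as a sensitivity analysis.

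Section 9.5 makes severity the randomisation stratum (mild 17–25, moderate 11–16, severe 10 or less) and aims for roughly equal numbers in each. Section 14.5.4 carries the SEP model over to several secondary endpoints, which "will be analysed using ANCOVA as described for the primary endpoint analysis for SEP Questions 2 and 3".

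**The concern.** Cutting a continuous baseline score into three groups discards the differences between men in the same group. If those differences predict the change in SEP percentage beyond what the SEP baseline predicts, the planned models leave some residual variance unexplained that an already collected value could remove.

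The point concerns the endpoints where precision counts most. Efficacy requires all three co-primary endpoints to be significant, and the two SEP questions have the smallest assumed standardised effects: 11.5/33 = 0.35 and 12/33 = 0.36, against 3.2/5.6 = 0.57 for IIEF-EF. The SEP baseline is also a fairly noisy covariate for some men, since it may rest on as few as four yes/no answers.

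**Working it through.** **Inputs (section 14.7 unless stated).** n = 250 per arm. Differences: "for IIEF-EF is 3.2, for SEP Question 2 is 11.5 and for SEP Question 3 is 12". SDs: "assumed to be 5.6, 33 and 33 for IIEF-EF, SEP Question 2 and Question 3, respectively". Correlations between endpoints: 0.5, 0.5 and 0.6. Test level (section 14.5.3): "Each comparison will be carried out at the two-sided 5% level of statistical significance after a Bonferroni correction (p-values multiplied by three"), so two-sided 0.05/3 = 0.0167 per dose and z = 2.394.

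**Step 1: the plan's own figure.** Section 14.7 says the sample size "provides 90% study power to reject the null hypotheses for all three primary endpoints when comparing a MED2005 dose to placebo". With SE = SD × √(2/250) and marginal power = Φ(difference/SE − 2.394):

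| Endpoint | SE | Difference/SE | Marginal power |
|---|---|---|---|
| IIEF-EF | 0.501 | 6.389 | 99.997% |
| SEP Question 2 | 2.952 | 3.896 | 93.3% |
| SEP Question 3 | 2.952 | 4.066 | 95.3% |

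The trivariate normal probability of rejecting all three is 90.4%, so the stated 90% reproduces. The smallest n per arm that reaches 90% is 248. The SEP endpoints set the joint power.

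**Step 2: how much of IIEF-EF the categories leave out.** Assume one third of men per stratum and scores evenly spread within each.

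- Severe stratum 1–10: within-stratum variances 8.25, 2.92 and 6.67, mean 5.9; total variance 46.0; share unused 5.9/46.0 = 12.9%.
- Severe stratum 6–10: within-stratum variances 2.00, 2.92 and 6.67, mean 3.9; total variance 32.25; share unused 12.0%.

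The second case is the more realistic. In Appendix 18.1, zero on Q1–Q5 means no sexual activity or no attempt, and Q15 starts at 1. Men with fewer than four screening attempts are excluded. Consistent answers therefore give at least 5 × 1 + 1 = 6.

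**Step 3: reduction in SEP residual variance.** Let ρ be the correlation of baseline IIEF-EF with SEP change given the SEP baseline, and w the share of IIEF-EF variation that the categories miss. Then, approximately,

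reduction = ρ²w / (1 − ρ²(1 − w)).

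With ρ = 0.3 and w = 0.129 this is 0.0116/0.9216 = 1.3%. Because w should also be taken given the SEP baseline, it grows as IIEF-EF and the SEP baseline become more correlated. A large-sample simulation allows for this (300,000 men per setting; severe stratum 1–10; linear relation; site omitted; IIEF-EF/SEP-baseline correlation 0.3 to 0.8):

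| Assumed ρ | Reduction in residual variance | Equivalent men per arm |
|---|---|---|
| 0.1 to 0.3 | 0.1% to 2.8% | 0.4 to 7 |
| 0.4 | 2.5% to 5.2% | 6 to 13 |
| 0.5 (extreme) | 4.6% to 8.9% | 11 to 22 |

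Simulations that generate SEP answers from a latent erectile function, with the severe floor at 6, gave 0.5% to 3.5%; the upper end needed a small IIEF-EF measurement error (SD 2). A working range of 0.1% to 3.5% follows, and 250 × 0.035 = 8.75, or at most about 9 men per arm.

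**Step 4: effect on joint power.** Section 14.7 does not say whether 33 is a raw or a residual SD.

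- If 33 is the residual SD of the planned model, multiplying the SEP variances by 0.999 gives 90.4% and by 0.965 gives 91.6%.
- If 33 is the raw SD of change, the planned covariates already reduce it. As an illustration, take residual variance at 0.7 of 33². Joint power is then 98.3% as planned and 98.6% after a further 3.5% cut.

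**The case against.** The strongest reply is that nothing here is wrong. An endpoint's own baseline plus the stratification factor is a conventional and valid ANCOVA. The three categories already capture about 87% to 88% of the IIEF-EF variance under the assumptions above, and the SEP percentage is a further continuous covariate. The stated power is met without the extra term. All of this stands, and it limits the point to an optional improvement.

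Three stronger readings are tempting and should not be drawn:

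- **That section 14.5.3 contradicts itself** by treating IIEF-EF one way in one model and another way in the others. It does not. One rule covers all three models: the endpoint's own baseline, plus the stratification factor unless that factor is redundant.
- **That the loss is clearly large**, say 5% or more of residual variance. This needs ρ of about 0.4 to 0.5. The correlations in section 14.7 are between endpoints, and none links baseline IIEF-EF to SEP change given the SEP baseline. Nor can 33 be taken as the raw SD to calibrate a simulation and then as the residual SD to compute power. Four attempts at 50% success give an SEP baseline standard error of 25 points (√(0.25/4) = 0.25), but that pairs the fewest allowed attempts with the most variable success rate and is not typical of every man.
- **That the secondary endpoints lose precision to the same degree.** They share the model, but no loss for SEAR, PGI-S or the other IIEF domains has been calculated.

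What remains is that the score is available, the term introduces no bias under randomisation, and the SEP endpoints limit joint power.

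**Conclusion.** The planned SEP models are valid but slightly less efficient than they could be. Adding the continuous Visit 2 IIEF-EF plausibly lowers SEP residual variance by 0.1% to 3.5%. For joint power per dose that is at most about 1.2 points (90.4% to 91.6%) if 33 is a residual SD, and about 0.3 of a point at most in the illustration where 33 is a raw SD.

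These figures rest on roughly equal strata, evenly spread scores within strata, an approximately linear relation and an assumed partial correlation that the documents do not give. The direction is secure if IIEF-EF predicts SEP change within strata; the size is not. The 90% power claim does not depend on the change. This is a minor, optional improvement, not an error or a contradiction.

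**What to change.** Before unblinding, add the Visit 2 IIEF-EF score as a continuous covariate to the primary ANCOVA for SEP Questions 2 and 3 in section 14.5.3 and the synopsis. Keep the SEP baseline, site and the severity category: the category is the stratification factor and belongs in the model. The same term may optionally be added to the secondary models in section 14.5.4 that copy this specification.

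The cost is one sentence and one degree of freedom among about 1000 men. No new data are needed, because the stratum is already computed from this score. Because section 14.5.3 spells the model out, a SAP that follows it would inherit the category-only form unless the change is made explicitly.
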